5.5.2. Main Analytical Approach

Time to Clinical Improvement

Time to clinical improvement will be presented by treatment group, using the Kaplan-Meier estimator. A Cox proportional hazards model with treatment, remdesivir strata (yes/no) and age (years) as covariates will be used to estimate the hazard ratio and compare treatment groups. Additional covariate's (i.e., Country (USA, Brazil), Chloroquine or hydroxychloroquine use (yes vs no), HIV anti-viral drug use (yes vs no), corticosteroid use (yes vs no) and azithromycin use (yes vs no)) may also be included if these are found to influence the treatment effect, based on observing p-value of < 0.05 for the covariate, after adjusting for the others in the model. The

stepwise selection procedure will be used to assess the additional covariates. In addition, the log rank test and stratified log rank test, with remdesivir as the strata, will be provided. The primary analysis will be conducted using the FAS.

Change from baseline to Day 10 or hospital discharge if sooner, in the ratio of hemoglobin oxygen saturation to inspired oxygen fraction (SpO₂/FiO₂)

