The primary efficacy endpoint of change from baseline to Day 10 or hospital discharge if sooner, in the ratio of hemoglobin oxygen saturation to inspired oxygen fraction (SpO₂/FiO₂) will be analyzed using a mixed model for repeated measures (MMRM). The Kenward-Roger method will be used to calculate the denominator degrees of freedom for the test of fixed effects and adjusted standard errors. The model will contain treatment, time and the treatment by time interaction as fixed effects and baseline score, age (years), corticosteroid use (yes vs no) and remdesivir strata as covariates. If age and/or corticosteroid use are not significant at the 5% level, they will be removed from the model. As the follow-up visit schedule for each participant will be variable, the following timepoints will be used; Day 1, Day 2, Day 3, Day 4, Day 5 and Day 10/Discharge. Additional time points (e.g., Days 6-9) may be included if most participants are not discharged prior to Day 10. An unstructured covariance matrix will be assumed to model the within-participant errors. This variance-covariance matrix will be estimated across treatment groups. However, if there is a convergence problem with the unstructured covariance matrix, then alternative covariance structures will be examined (heterogeneous Toeplitz structure, Compound Symmetry) and the one with the best fit as determined by the Akaike information criteria (AIC) (i.e., smallest AIC value) will be used. The least squares means (LS-means) for each treatment, LS-means treatment difference and corresponding confidence interval (CI) for the LS-means difference and p-value for the treatment difference, will be reported at the Day10/Discharge timepoint.

The primary analysis will be conducted using the FAS.

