5.5.3. Sensitivity Analysis

Time to Clinical Improvement

The following sensitivity analyses will be conducted:

- 1) The primary analysis will be repeated for the PP analysis set.

Change from baseline to Day 10 or hospital discharge if sooner, in the ratio of hemoglobin oxygen saturation to inspired oxygen fraction (SpO₂/FiO₂)

The following sensitivity analyses will be conducted:

- 1) The primary analysis will be repeated for the MITT analysis set.
- 2) The primary analysis will be repeated for the PP analysis set.

Depending on the amount of missing data, additional sensitivity analyses may be needed. If these are needed, they will be documented in the CSR.

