5.9.3. Subgroup Analyses

The following sub-groups will be examined for the primary endpoints. Results will be displayed in both tabular form and graphical form using a forest plot.

- Age (≤ 65 vs > 65)
- Gender (male vs female)
- Remdesivir Use within 24 hours of Randomization (yes vs no)
- Country (USA, Brazil)
- Corticosteroid Use (e.g., Dexamethasone) (yes vs no)
- Patients with a positive PCR test at baseline vs not positive.
- Patients with IL-6 $>$ median at baseline vs \leq median

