5.9.6. Concomitant Medications

Concomitant medications are those that are taken at any time after the first dose of study medication.

If the start day of a medication is missing, then if the month and year of the start date are on or after the date of randomization, the following rules will be applied:

- If month/year of the start date is equal or after the month/year of the date of randomization, the medication will be considered concomitant;
- If month/year of the start date is equal to the month/year of the date of randomization, and the end date is present, the end date will be used to determine if the medication stopped prior to randomization or after. If the end date is after, the medication will be considered concomitant; otherwise, if the medication stopped prior, then it will be considered to be prior;
- If month/year of the start date is equal to the month/year of the date of randomization, and the end date is a partial date, the medication will be considered concomitant;
- If, despite implementing the above conventions, the start date of the medication cannot be placed before, on, or after randomization, then the medication will be considered concomitant.

Concomitant medications will be coded using the World Health Organization (WHO) Drug Dictionary and summarized by drug class (ATC Level 3) and preferred term for each treatment group. The summaries will present the number and percentage of participants using each medication by treatment group and overall. Participants may have more than one medication per drug class or preferred term. At each level of summarization, a participant is counted once if he/she reported one or more medications at that level. No statistical hypothesis tests will be performed.

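### Drug-use covariates in both primary models are selected by p-value and carry no time window, so on-study drug use could enter the primary estimates

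*SAP*

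**What the plan says.** For time to clinical improvement, SAP 5.5.2 always keeps treatment, remdesivir stratum and age in the Cox model. Country and use of chloroquine/hydroxychloroquine, HIV anti-virals, corticosteroids and azithromycin "may also be included if these are found to influence the treatment effect". Selection is stepwise, and the SAP gives the criterion for entry as "based on observing p-value of < 0.05 for the covariate, after adjusting for the others in the model". The section also promises tests without selection: "In addition, the log rank test and stratified log rank test, with remdesivir as the strata, will be provided".

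For SpO2/FiO2, the same section keeps baseline and remdesivir stratum in the MMRM and tests the other two covariates: "If age and/or corticosteroid use are not significant at the 5% level, they will be removed from the model". Corticosteroid use is its only drug-use term.

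None of these drug-use terms is dated. The subgroup list in SAP 5.9.3 dates one exposure, "Remdesivir Use within 24 hours of Randomization (yes vs no", but not another in the same list, "Corticosteroid Use (e.g., Dexamethasone) (yes vs no". SAP 5.9.6 separates prior from concomitant use ("otherwise, if the medication stopped prior, then it will be considered to be prior"), but for the medication tables; 5.5.2 does not refer to it.

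Protocol 5.1.2 excludes patients on chloroquine or hydroxychloroquine at entry. Protocol 6.6.2 only restricts these drugs afterwards. Protocol 9.4.2 already allowed drug-use effects into the primary model at discretion. The SAP Version History records that version 2.0 clarified the stepwise procedure and added corticosteroid use as a candidate in all models.

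**The concern.** A covariate in a randomized comparison should be fixed at randomization. A yes/no indicator of drug use at any time on study is not. A patient who recovers early has less time to start the drug, so the indicator is tied to outcome even when the drug does nothing. If treatment speeds recovery, the indicator also differs by arm, and adjusting for it removes part of the treatment effect.

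The entry rule makes this more likely. The stated reason for entry is influence on the treatment effect, but the test is whether the covariate itself predicts outcome. A marker of a long stay passes that test almost every time.

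The chloroquine/hydroxychloroquine term shows the problem most clearly. Current use at entry is an exclusion, so in an eligible patient a yes means use started on study or a course stopped before entry.

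At stake are the power and interpretation of both primary estimates. Either one alone can make the study a success (SAP 2).

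**Working it through.** **The plan's own figures.** From SAP 3: two-sided 5%, 80% power, control fraction 1/3, hazard ratio 0.5. Reading θ as the log hazard ratio, events = (1.960 + 0.842)² / [(1/3)(2/3)(ln 0.5)²] = 73.5, so 74. Power at 75 events = Φ(√(75 × 2/9) × 0.693 − 1.960) = Φ(0.870) = 80.8%. For SpO2/FiO2, N = (1.960 + 1.282)² / [(2/9)(0.625)²] = 121.0, and power at 80 vs 40 is 89.8%. Both stated figures reproduce.

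**Mechanism.** Below, a hazard ratio above 1 means faster recovery. Take a placebo median of 13.5 days (midpoint of the plan's 12-15) and a true hazard ratio of 2. Recovery hazards are ln 2/13.5 = 0.0513 per day on placebo and 0.1027 on active. Let an inert drug be started at s = 0.05 per day in both arms (assumed; the documents give no rate). The chance of starting before recovery and before Day 28 is s/(s + h) × [1 − exp(−28(s + h))]:
- placebo: 0.493 × (1 − 0.059) = 46%
- active: 0.327 × (1 − 0.014) = 32%

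Identical prescribing of a drug with no effect gives different use by arm, because treatment shortens the stay.

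**Events.** The same inputs give 40 × (1 − e^−1.438) + 80 × (1 − e^−2.875) = 30.5 + 75.5 = 106 events by Day 28, well above the planned 75. To see results near 75, the placebo median was set to 31 days: 40 × 0.465 + 80 × 0.714 = 18.6 + 57.1 = about 76.

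**Cox simulation.** 80 vs 40, exponential recovery, censoring at Day 28, one-sided 0.025. Treatment, remdesivir and age are forced. Corticosteroid use and four inert baseline candidates are removed backward until every p < 0.05. Mostly 4000 trials per setting. Ranges cover start rates, repeat runs, or both.

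| Setting | No drug term | SAP rule |
|---|---|---|
| True HR 2, starts to Day 28, 3% per day | 90% power, HR 2.02 | 83-84%, HR 1.95 |
| 5% per day | 90%, HR 2.02 | 81%, HR 1.90 |
| 8% per day | 90%, HR 2.02 | 75-77%, HR 1.86 |
| 30% on drug at baseline plus 5% per day later, counted together | 90% | 85% |
| Starts counted in first 10 days only | 90% | 88-90% |
| Starts counted in first 5 days only | 90% | 90% |
| Baseline-only term | 90% | 90% |
| About 76 events, 3-8% per day to Day 28 | about 75% | 65-71% |
| About 76 events, baseline-only term | 75% | 75% |
| Null, equal starts to Day 28 | HR 1.00, error 0.025-0.026 | HR 1.00, error 0.032-0.040 |
| Null, baseline-only term | error 0.026 | error 0.027 |
| Null, treatment doubles starts (5-6% per day on placebo) | HR 1.00 | HR 1.37-1.43, error 27-32% |
| Null, treatment halves starts (5-6% per day on placebo) | HR 1.00 | HR 0.75-0.81, error about 0.2% |

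With starts counted to Day 28 at equal rates and a true HR of 2, the drug term was selected in 98-100% of trials.

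**MMRM simulation.** Unstructured covariance, Days 2-5 and Day 10/discharge, SD 40, correlation 0.7, true difference 25, discharge made faster by improvement, starts at 3-8% per day to Day 28.
- Effect present from Day 2: estimate 25.0 without the term, 21.9-23.3 with the rule; power 89% vs 82-85%.
- Effect building to Day 5 or linearly to Day 10: at most 0.7 points lower; power 89-90% vs 88-89%.
- Starts limited to the first 10 days: 0-2 points lost. Baseline-only: none.
- Null with equal starts: difference 0, type I error not raised.

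The MMRM pattern depends on the assumed link between improvement and discharge.

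**The case against.** The strongest reply is that corticosteroid use in SAP 5.9.3 sits among age, gender, country, baseline PCR, baseline IL-6 and remdesivir near randomization, so a baseline meaning is the natural one and counting to Day 28 is the widest reading. This has force: under a baseline meaning nothing is lost, and a 10-day window costs little. But the list does not define the term, and a baseline meaning leaves the chloroquine/hydroxychloroquine term nearly empty.

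Second, p-value selection does no measurable harm here in its own right. With a baseline-only term, power and type I error are unchanged. That stands. Fixing the models is sound practice, but the quantified loss comes from timing.

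Third, the two log-rank tests show the time-to-improvement result without covariate selection. That stands for this endpoint. SpO2/FiO2 has no such check: apart from "The primary analysis will be repeated for the MITT analysis set" and the same for the per-protocol set, SAP 5.5.3 commits to nothing.

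Fourth, version 2.0 made these covariate choices deliberately, in a revision that cites FDA comments. The rationale cells beside the covariate changes are blank, so the documents do not show whether FDA asked for them.

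**Conclusion.** The concern holds as a gap in definition with a real consequence. Undated drug-use terms can enter or stay in both primary models on a rule that favours markers of a long stay.

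A reader might infer that the SAP plans to adjust for post-randomization drug use. It does not say so; it leaves timing open. A reader might also infer that the primary test is invalid under the null. With equal drug starts in both arms, the null estimate stays unbiased, with a one-sided Cox error of about 0.03-0.04. Bias under the null needs treatment to change drug starts, and the documents give no evidence that it does.

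If on-study use is counted to Day 28 with equal starts, a true benefit is attenuated: Cox power about 90% vs 75-84% at about 106 events, or about 75% vs 65-71% near the planned 75. The MMRM loses 0 to about 3 of 25 points; in these runs the loss was material only when the effect was present early. All start rates, and the doubling and halving, are assumptions. The point is worth correcting, but it does not undermine the design.

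**What to change.** - Define every drug-use covariate in the primary models as use at or before randomization. Remove chloroquine/hydroxychloroquine from the candidates.
- Fix both primary models, with no entry or removal by p-value. Cox: treatment, randomized remdesivir stratum, age. MMRM: treatment, time, treatment-by-time, baseline ratio, randomized remdesivir stratum, age. These are the base models of protocol 9.4.2 without its discretionary clause, and with the randomized stratum in place of remdesivir use.
- If the sponsor keeps corticosteroids, include baseline corticosteroid use in both models whatever its p-value. Put no other drug-use term in the primary models.
- Apply the same pre-randomization definition to the corticosteroid stratum of the CMH tests in SAP 5.6.2 and 5.7. Use the same fixed Cox model for time to discharge readiness (SAP 5.6.2).
- Describe post-randomization drug use by arm.

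The cost is a SAP edit and the protocol amendment that SAP 1 and protocol 9.4 call for, since a primary analysis changes. A small loss of precision is possible if a prognostic covariate is dropped. No new data are needed: protocol 6.6 already records medications from the 30 days before first dose.

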9.4.2. Efficacy Analyses

The primary efficacy endpoint of time to clinical improvement will be presented using the Kaplan-Meier estimator. Subjects will be censored at Day 28 or earlier, if they discontinue the study prior to observing the event. A Cox proportional hazards model with treatment, remdesivir use (yes/no) and age as covariates will be used to estimate the hazard ratio and compare treatment groups.

The primary efficacy endpoint of change from baseline to Day 10 or hospital discharge if sooner, in the ratio of hemoglobin oxygen saturation to inspired oxygen fraction ($\text{SpO}_2/\text{FiO}_2$) will be analyzed a mixed measures repeated model (MMRM). The Kenward-Roger method will be used to calculate the denominator degrees of freedom for the test of fixed effects and adjusted standard errors. The model will contain treatment, time and the treatment by time interaction as fixed effects and baseline score, age, and remdesivir drug use (yes vs no) as covariates. An unstructured covariance matrix will be assumed to model the within-participant errors.

Sub-group analyses for the two primary endpoints will also be conducted for the following sub-groups: Chloroquine or hydroxychloroquine use (yes vs no), HIV anti-viral drug use (yes vs no) and azithromycin use (yes vs no). If warranted, these effects may be included in the primary model.

No adjustment for multiplicity among the two primary endpoints will be made, as this is a Phase 2 study. Secondary endpoints will be analyzed without adjustment for multiplicity. All efficacy analyses will use the FAS analysis set, and MITT analysis set if applicable.

Secondary endpoints that are defined as time to event endpoints will be analyzed using survival analysis methods. Data will be presented using the Kaplan-Meier. Subjects will be censored at Day 28 or earlier, if they discontinue the study prior to observing the event. A Cox proportional hazards model with treatment, remdesivir use (yes/no), and age as covariates will be used to estimate the hazard ratio and compare treatment groups.

Secondary endpoints that are defined as proportions will be summarized using frequency counts and proportions. Treatment groups will be compared using a Cochran–Mantel–Haenszel (CMH) test stratified by remdesivir use (yes vs no). Additional covariates may be included if warranted.

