5.6. Secondary Endpoint(s) Analysis

5.6.1. Key/Confirmatory Secondary Endpoint(s)

Change from baseline in serum calprotectin

Both the observed value and the change from baseline value will be summarized. Participants who are discharged prior to day 10, will have their end of treatment assessment, mapped to day 10.

To compare the change from baseline over time a MMRM model will be used. Missing data will be assumed to be missing at random and maintained as missing. The Kenward-Roger method will be used to calculate the denominator degrees of freedom for the test of fixed effects and adjusted standard errors. The model will include baseline value as a covariate, treatment, visit and visit-by-treatment interaction terms as categorical fixed effects, and participant as a random effect. An unstructured covariance matrix will be assumed to model the within-participant errors. This variance-covariance matrix will be estimated across treatment groups. However, if there is a convergence problem with the unstructured covariance matrix, then alternative covariance structures will be examined (heterogeneous Toeplitz structure, Compound Symmetry) and the one with the best fit as determined by the Akaike information criteria (AIC) (i.e., smallest AIC value) will be used. The least squares means (LS-means) for each treatment, LS-means treatment difference and corresponding confidence interval (CI) for the LS-means difference and p-value for the treatment difference, will be reported at each visit. For each parameter, a plot of the LS-means (and 95% CI), over time and by treatment group, will be produced.

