5.7. Tertiary/Exploratory Endpoint(s) Analysis

The following exploratory endpoints will be analyzed using the FAS without adjustment for multiplicity.

Proportion of participants requiring mechanical ventilation after study entry

The frequency and proportion of participants will be reported by treatment group. The difference between treatment groups will be compared using a Cochran-Mantel-Haenszel (CMH) test stratified by Country (USA, Brazil), age (≤ 65 vs > 65), corticosteroid use (yes vs no) and remdesivir strata (yes, no). The common risk difference and two-sided 95% stratified Newcombe confidence interval will be reported. The strata will be weighted using Mantel-Haenszel weights.

Change from baseline in SARS-CoV-2 viral load at Days 10/EOT, 14, 21 and 28

The change from baseline to each of days 5, 10, 14, 21 and 28 in the SARS-CoV-2 viral load will be derived by taking the SARS-CoV-2 viral load at the post baseline timepoint (i.e., Days 10, 14, 21 and 28) and subtracting the baseline SARS-CoV-2 viral load. Participants who are discharged prior to day 10, will have their end of treatment assessment, mapped to day 10. Missing data will be assumed to be missing at random and this endpoint will be analyzed using likelihood-based methods, therefore missing data will be maintained as missing. The change from baseline to each of days 5, 10, 14, 21 and 28 in the SARS-CoV-2 viral load will be

analyzed using a mixed model for repeated measures (MMRM) approach as outlined for the co-primary endpoint of change from baseline in SpO₂/FiO₂ ratio. The data may be log transformed prior to analysis if the assumptions of normality are violated. For values below the limit of quantification, half the value between 0 and the limit of quantification will be used. This analysis will only be conducted for patients who are positive at baseline based on PCR testing.

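### The primary SpO2/FiO2 MMRM fits one baseline slope to all modelled days, so the Day 10/Discharge contrast is likely under-adjusted for baseline and loses some precision

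*SAP*

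**What the plan says.** SAP 5.5.2 gives the model terms for change in SpO2/FiO2 as "treatment, time and the treatment by time interaction as fixed effects and baseline score, age (years), corticosteroid use (yes vs no) and remdesivir strata", the last four being covariates. Age and corticosteroid use are dropped if not significant at 5%. Protocol 9.4.2 has the same structure: "treatment, time and the treatment by time interaction as fixed effects and baseline score, age, and remdesivir drug use (yes vs no) as covariates". Neither contains a baseline-by-time term.

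On timing, SAP 5.5.2 states that "the following timepoints will be used; Day 1, Day 2, Day 3, Day 4, Day 5 and Day 10/Discharge", and that "Additional time points (e.g., Days 6-9) may be included if most participants are not discharged prior to Day 10". On covariance: "An unstructured covariance matrix will be assumed to model the within-participant errors". The treatment difference, its interval and its p-value "will be reported at the Day10/Discharge timepoint".

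SAP 5.5.1 maps the end-of-treatment assessment of participants discharged early to Day 10. The sensitivity analyses in SAP 5.5.3 repeat the same model in the MITT and per-protocol sets, and SAP 5.5.4 lists no supplementary analyses. Nothing elsewhere frees the baseline slope.

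**The concern.** A model with treatment-by-time but no baseline-by-time assumes that baseline predicts the change equally on every modelled day. Several features of this plan make that doubtful.

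- **Early days.** The outcome is change from baseline. Soon after baseline few participants have moved, so the change depends little on where they started. The protocol's Schedule of Activities (Table 2) places baseline on Day 1.
- **Last timepoint.** It is Day 10 or the discharge value. Participants who have recovered to room air reach a similar ratio whatever their start, so a low baseline goes with a large gain and the slope is negative.
- **Range of baseline.** Eligibility (Protocol 5.1.1 and 5.1.2) runs from room air with SpO2 of 94% or less to FiO2 below 0.75. At SpO2 94% that is a ratio from 94/0.21 = 448 down to about 94/0.75 = 125, so baseline could carry much of the outcome.
- **Weighting.** Five of the six timepoints are Days 1 to 5. Where residual variance is small on those days, the unstructured covariance gives them most of the weight in the common slope.

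At stake is the standard error of one of two primary contrasts, in a trial with 40 controls.

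**Working it through.** **1. The plan's own power.** Inputs from Protocol 9.2 and SAP Section 3: 80 active, 40 control, SD 40, difference 25, two-sided 5%.

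- SE = 40 × √(1/80 + 1/40) = 7.75. Power ≈ Φ(25/7.75 − 1.96) = Φ(1.27) = 89.8%.
- SAP formula: N = (1.960 + 1.282)² / [(1/3)(2/3)(0.625²)] = 121.

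The stated figures of about 90% and 120 reproduce. They rest on an unadjusted two-sample t-test and do not depend on the baseline slope.

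**2. What a common slope does.** Let b_t be the true slope of change on baseline at day t, R the covariance of the changes given baseline, R_10 its Day 10 variance and V_0 the baseline variance. In large samples with complete data:

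- fitted common slope: g = (1′R⁻¹b) / (1′R⁻¹1)
- Day 10 variance per participant, common slope: R_10 + (b_10 − g)² V_0
- Day 10 variance per participant, with baseline-by-time: R_10

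**3. One case in full.** Assumptions, not in the documents: SD 40 on every day, first-order autoregressive correlation 0.9 per day, Day 1 response half a day after baseline.

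- Slopes at Days 1, 2, 3, 4, 5, 10: −0.05, −0.10, −0.19, −0.27, −0.34, −0.61. Fitted common slope g = −0.09.
- R_10 = 1600 × (1 − 0.387²) = 1360.
- Common-slope variance = 1360 + (0.613 − 0.091)² × 1600 = 1360 + 436 = 1796. Ratio 1.32.
- Power for a difference of 25: SE 8.20 gives 86.2%; with baseline-by-time, SE 7.14 gives 93.8%.

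**4. Range over assumptions** (variance with common slope divided by variance with baseline-by-time).

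| Assumed pattern | Day 1 a response | Day 1 left out |
|---|---|---|
| Autoregressive, baseline-to-Day-10 correlation 0.63 / 0.39 / 0.23 / 0.13 | 1.19 / 1.32 / 1.39 / 1.40 | 1.15 / 1.24 / 1.26 / 1.24 |
| Autoregressive plus measurement noise | 1.10–1.19 | 1.08–1.14 |
| Noise, with SD growing from 30 to 40 | 1.02–1.10 | 1.02–1.08 |
| Recovery curves, median recovery 13.5 / 8 / 5 days | 1.07 / 1.12 / 1.19 | 1.03 / 1.06 / 1.08 |
| A second set of recovery curves | 1.06–1.23 | 1.06–1.13 |
| Same correlation on every day | 1.00 | 1.00 |

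The first recovery row comes from 1,500 simulated trials per setting (80:40, baseline FiO2 0.21 to 0.70, exponential recovery, no drug effect). Its Day 10 slopes were −0.43 to −0.76, against fitted common slopes of −0.09 to −0.35.

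In the four autoregressive cases with Day 1 included, power was 96.8 / 86.2 / 80.4 / 78.7% with the common slope and 98.6 / 93.8 / 91.3 / 90.3% with baseline-by-time.

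**5. Bias and standard error.** 1,500 simulated trials, true difference 25, SD 40, baseline-to-Day-10 correlation 0.35, noise and Day 1 included:

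| Model | Mean estimate | Empirical SD | Mean model SE | Power |
|---|---|---|---|---|
| Common slope | 24.77 | 7.97 | 7.93 | 87.7% |
| Baseline-by-time | 24.82 | 7.25 | 7.27 | 92.7% |

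Both are unbiased, and both model standard errors match the actual spread.

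**The case against.** The strongest reply is that this is a choice about efficiency, not an error. That stands. Randomization protects the contrast, the reported standard error already covers the extra scatter, and type I error is not inflated.

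The reply also limits the size, and several stronger readings fail.

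- **That the slope must differ by day.** The documents do not establish this. With equal correlation on every day nothing is lost. Noise from pulse oximetry and from the stepwise flow-to-FiO2 table (SAP 5.5.1) makes even the early slope negative through regression to the mean, which narrows the gap.
- **That Day 10 is left essentially unadjusted.** Not in general. A fitted slope of −0.35 against a true −0.76 makes 0.35/0.76 = 46% of the adjustment.
- **That chance baseline imbalance shifts the result by a large part of the planned 25.** This needs a baseline SD of about 85, assumed in the recovery simulation, set against a difference planned on SD 40. At SD 40 the chance imbalance has SD 7.7. With 0.35 to 0.45 points of shift per point of imbalance, as in that simulation, the shift is 2.7 to 3.5 points, and the standard error includes it.
- **That power falls below the plan.** It does in some cases and not in others: 96.8% under one common-slope case.
- **That the other repeated-measures models lose as much.** The calprotectin model (SAP 5.6.1) reads "The model will include baseline value as a covariate, treatment, visit and visit-by-treatment interaction terms as categorical fixed effects", and viral load (SAP 5.7) follows the "approach as outlined for the co-primary endpoint of change from baseline in" SpO2/FiO2. They share the omission, but their endpoints have no Day 1 to 4 series, and no gain has been calculated for them.

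Part of the loss also comes from modelling Day 1 as a response. The SAP is unclear here: Table 2 of the protocol makes Day 1 the baseline day, while SAP 5.2 lists Baseline and Days 1 to 9 separately. Without Day 1 the loss is smaller but does not vanish in the decaying-correlation or recovery cases.

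**Conclusion.** The omission is certain from the text of both documents. Its likely effect is that the only reported SpO2/FiO2 contrast is under-adjusted for the baseline value. The cost is precision, not validity.

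The size cannot be taken from the documents. Under plausible recovery or noise assumptions the variance is roughly 3 to 20% higher, or about 3 to 13% if Day 1 is not a response; single scenarios fall slightly outside these ranges. Strong autoregressive decay takes it to about 40%, a standard error about 18% larger (√1.40 = 1.18). It is zero if the baseline slope is equal at every modelled day.

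The calculations assume complete data and use no estimated correlations from this population. The change is worth making because it is nearly free, not because the planned analysis is invalid.

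**What to change.** In SAP 5.5.2, and to match in Protocol 9.4.2, specify: treatment, time, treatment-by-time, baseline, baseline-by-time, and the remaining covariates as now. With six timepoints this adds five fixed-effect parameters; each optional day from 6 to 9 would add one more. No new data are needed and the estimand does not change.

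State also whether Day 1 is baseline or a post-baseline response. If the Day 1 record is the baseline record, its change is identically 0 and the unstructured covariance matrix is singular, so Day 1 must leave the response vector. Baseline-by-time then costs four parameters.

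SAP Section 1 requires changes to the primary analyses to be documented by protocol amendment, so the administrative cost is a line in each document. The change should be fixed before anyone choosing the model sees results by arm. The same term may be added to the calprotectin, viral-load and IL-6/D-dimer models for consistency, without a claim of gain.
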